2.4. Sample Size Considerations

Given that the study population depends on the feeder studies, no sample size was determined for this study.

At the time that the feeder studies were stopped in March 2019, approximately 2600 participants had received treatment in 1 of the feeder studies. At the time of study planning, Biogen estimated that of these 2600 participants, approximately 2400 participants could be eligible based on inclusion and exclusion criteria to participate in Study 221AD304.

A total of 1865 participants were screened in study 221AD304 and were from studies 221AD301, 221AD302, 221AD103, and 221AD205. Of these, 1696 participants were enrolled across 305 sites globally.

3. Definitions

3.1. Dates and Points of Reference

- 1. Study Day 1: the date of the first dose of aducanumab in the study
- 2. Study Day
 - a. For a date on or after Study Day 1Study Day = (Date of Interest) (Study Day 1) + 1
 - b. For a date before Study Day 1Study Day = (Date of Interest) (Study Day 1)

3. First dose date and last dose date

The first dose date in the study is date of the first dose of aducanumab in 221AD304 study, the last dose date in the study is the date of the last dose of aducanumab in 221AD304 study.

Study: 221AD304 Version: 2.0

The first and last dose date in the core treatment period are the dates of the first and last dose of aducanumab received before scheduled Week 102 visit respectively.

The first and last dose date in LTE treatment period are the dates of the first and the last dose of aducanumab received after scheduled Week 102 visit.

4. End of Treatment (EOT)

EOT date for the study is the last dose date in the core treatment period for subjects who did not receive any aducanumab in scheduled LTE visits, or the last dose date in the LTE treatment period if subject had received at least one dose of aducanumab in scheduled LTE visits.

EOT date for the core treatment period is the last dose date in core treatment period.

EOT date for the LTE treatment period is the last dose date in LTE treatment period.

5. End of Study (EOS)

EOS date for the study is the End of Study date recorded on the End of Study eCRF page. If the EOS date is missing, then the EOS date will be imputed using the very last date of any assessment done as completed in RAVE or in any vendor database if the EOS date is missing.

For subjects who received the aducanumab in LTE visits, the EOS date for the core treatment period is defined as one day before the first dose date in LTE treatment period and those subjects will be considered as completer for the core treatment period. Otherwise, the EOS date for the core treatment period is the same as the EOS date for the study.

According to the eCRF Completion Guidelines, the End of Study eCRF must be completed for every subject enrolled in the study. For subjects who did not enter Long-Term Extension (LTE): A Completer is a subject who completed all visits as mandated by protocol inclusive of the Week 102 EOT visit and the Week 118 FU visit. A subject who discontinued treatment early and remains in study in the protocol specific follow schedule, inclusive of Week 102, is also considered as Complete.

For subjects who entered LTE: A Completer is a subject who completed all visits as mandated by protocol inclusive of the Week 154 EOT visit and the Week 170 FU. A subject who discontinued treatment early and remains in study in the protocol specific follow schedule, inclusive of Week 154, is also considered as Complete.

6. Visit window for by-visit analysis

For data that are summarized by visit, assessment from all scheduled visits and unscheduled visits will be mapped to an appropriate analysis visit using a windowing scheme as described in each section.

Unless otherwise specified, if there is more than 1 value in the same analysis visit window for a certain parameter for a participant, then the closest record to the target

Study: 221AD304 Version: 2.0

visit day will be used for the by visit analysis. If there are 2 values in the same analysis visit window with the same distance from the target visit day for a certain parameter for a participant, then the record with the later date will be used for the by visit analysis. If there are 2 values on the same day for a certain parameter for a participant, then the record with the later time will be used for the by visit analysis.

- 7. Baseline values is defined as the most recent non-missing measurement collected prior to the first dose in the study or as the last non-missing measurement collected during screening for subjects not dosed.
- 8. Change from 221AD304 baseline will be defined as post-baseline value minus 221AD304 baseline value.
- 9. Percent change from baseline will be defined as post-baseline value minus baseline value then divided by baseline value.

10. Treatment Emergent

An adverse event is regarded as treatment emergent if the event has onset date/time on or after the first dose date/time of study treatment, or was reported prior to the first dose and subsequently worsens in severity after first dose date. Additional criteria to determine treatment emergent are described in Section 5.7.2.1.

3.2. Study Treatment

During the Core Treatment Period, participants will receive IV infusions of aducanumab approximately Q4W for a duration of 100 weeks (a total of 26 doses). The aducanumab dosing regimen will be 10 mg/kg following this titration: 1 mg/kg for the first 2 doses, 3 mg/kg for the next 2 doses, 6 mg/kg for the next 2 doses, and 10 mg/kg thereafter. Eligible participants will then enter the LTE treatment period and continue dosing on 10 mg/kg aducanumab Q4W for an additional 52 weeks (a total of 152 weeks of continuous treatment).

The safety analysis groups are defined based on historical exposure of BIIB037 in feeder studies including 0 dose of BIIB037, pre-treated with BIIB037 with 0 dose of 10 mg/kg, and with >0 dose of 10 mg/kg.

3.3. Study Treatment Periods

• Core period

For subjects who received at least one dose of study treatment in LTE visits, core period is from the first dose of treatment in the study to before the first dose date in LTE period. For subjects who did not receive any dose in any LTE visits, core treatment period is from the first dose in study to the very last date of any assessment done as completed in RAVE or in any vendor database.

• Long-term extension period

Study: 221AD304 Version: 2.0

Long-term extension period, also called LTE period, is from the first dose date in LTE treatment period to the very last date of any assessment done as completed in RAVE or in any vendor database.

3.4. Key Derived Variables

This section is not applicable.

3.5. Stratification Factors and Subgroup Variables

3.5.1. Stratification Factors

This section is not applicable.

3.6. Analysis Population

• Intent-to-treat and screen failure (ITTSF) population:

The Intent-to-treat and screen failure population is defined as all subjects screened including both enrolled and screen failure subjects.

• Enrolled population:

The enrolled population is defined as all subjects who signed informed consent, were assigned a subject identification number, and met the eligibility criteria for study 221AD304.

• Modified Intent-to-treat (mITT) population:

The modified Intent-to-treat population is defined as all subjects who received at least one dose of aducanumab in study 221AD304.

• Modified Intent-to-treat (mITT) population for core period:

The modified Intent-to-treat population for core treatment period is defined as all subjects who received at least one dose of aducanumab in the core period.

• Modified Intent-to-treat (mITT) population for LTE period:

The modified Intent-to-treat population is defined as all subjects who received at least one dose of aducanumab in the LTE period.

Study: 221AD304 Version: 2.0

• Safety population:

The safety population is defined as all subjects who received at least one dose of aducanumab in study 221AD304.

• Safety population for the core period:

The safety population is defined as all subjects who received at least one dose of aducanumab in the core period.

• Safety MRI population:

The safety MRI population is defined as all subjects who received at least one dose of aducanumab in study 221AD304 and had at least one post-baseline MRI assessment in study 221AD304.

• Safety MRI population for the core period:

The safety MRI population is defined as all subjects who received at least one dose of aducanumab in the core period and had at least one post-baseline MRI assessment in the core period.

• Immunogenicity population:

The analysis population for immunogenicity is defined as all subjects who received at least one dose of aducanumab in study 221AD304 and had at least one post-dose sample evaluated for immunogenicity.

• Immunogenicity population for the core period:

The analysis population for immunogenicity is defined as all subjects who received at least one dose of aducanumab in the core period and had at least one post-dose sample evaluated for immunogenicity in the core period.

4. List of Planned Study Analyses

4.1. Interim Analysis

According to the protocol, interim analyses may be conducted when the last patient is enrolled and when 50% of the enrolled patients have completed the study. Other interim analyses may be conducted at the discretion of the sponsor.

The following interim analyses in Table 3 occurred prior to the completion of the core treatment period:

Study: 221AD304 Version: 2.0

Table 3 Summary of Interim Analysis

[figure not shown]
Data	Focus of analyses	Amount of 221AD304 post- baseline data
Data cutoff of July 15th, 2021 (Baseline Analysis)	Gap period between feeder studies and 221AD304 baseline	NA
Data cutoff of March 15th, 2022	221AD304 post-baseline data (No analyses comparing to external control were done)	420 of 1675 (25%) participants from feeder studies 221AD301 and 221AD302 had an opportunity to complete the 221AD304 Week-78 visit
Data cutoff of August 15 th , 2022	First analysis of 221AD304 versus external control: • 221AD304 post-baseline data for participants from feeder studies 221AD301 and 221AD302. • A selected number of analyses will be performed including participants from feeder studies 221AD103 and 221AD205. • The focus of analyses will include the primary and secondary objectives as well as selected	 Approximately 1180 of 1675 (70%) participants from feeder studies 221AD301 and 221AD302 will have had an opportunity to complete the 221AD304 Week-78 visit. All but one participant will have had an opportunity to complete the 221AD304 Week-52 visit.

4.2. Primary Analysis

The primary analysis of Study 221AD304 focuses on the core primary endpoints described in Section 2.1.1 and will be performed after all subjects have completed the core treatment period, either by completing the Week 118 follow-up visit or by entering the LTE treatment period. At the time of announcement of early study termination on 19 September 2023, all subjects had completed the Week 102 visit and only a few subjects had not completed the Week 118 follow-up visit.

As described in Section 2.1, the core primary and LTE

Product: Aducanumab
Study: 221AD304
Statistical Analysis Plan
Version: 2.0

The core secondary objectives and endpoints (see Section 2.1.2) are not described in the protocol but were developed as part of an interim statistical analysis plan (version 2.0). This interim analysis used a data cutoff date of August 15th, 2022 (see Table 3) and comprised the primary efficacy analysis of study 221AD304 versus an external control using clinical endpoints and

The analysis of the secondary objectives and endpoints will be summarized in the 221AD304 (EMBARK) CSR addendum.

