2.1.2. Core Secondary Objectives and Endpoints

The core secondary objectives and endpoints are not described in the protocol but were developed as part of an interim statistical analysis plan (version 2.0)

The core secondary objectives defined in the interim SAP are:

[figure not shown]
- Evaluation of the efficacy of aducanumab versus an external control using clinical endpoints
- Evaluation of the efficacy of aducanumab versus an external control using

The corresponding primary clinical efficacy endpoint is change from baseline CDR-SB at Week 78.

Study: 221AD304 **Version:** 2.0

Additional core secondary clinical efficacy endpoints to be compared to an external control are:

- Change from baseline Alzheimer's Disease Composite Score (ADCOMS) at Week 78
- Change from baseline Alzheimer's Disease Assessment Scale, Cognitive subscale (ADAS-Cog 13) at Week 78
- Change from baseline Mini-Mental State Examination (MMSE) at Week 78

Product: Aducanumab

Study: 221AD304 Version: 2.0

Statistical Analysis Plan

Product: Aducanumab

Study: 221AD304

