5.1. General Principles

This statistical analysis plan (SAP) defines the analysis scope for the Primary Analysis and the Final Analysis.

Summary tables will be presented using descriptive summary statistics. For continuous variables, summary statistics will generally include: number of subjects with data, mean, standard deviation, median, 25% percentile, 75% percentile, minimum and maximum. For categorical variables, this will generally include: number of subjects randomized or dosed, number with data, and the percent of those with data in each category.

All analyses will be summarized by safety analysis groups (0 dose of BIIB037, pre-treated with BIIB037 with 0 dose of 10 mg/kg, >0 dose of 10 mg/kg, subtotal of pre-treated with BIIB037, and overall total; analysis display SA in Appendix 9), unless otherwise specified. Where indicated, the analyses will be repeated by safety analysis group stratified by

Study: 221AD304 Version: 2.0

As noted in Section 1, due to the early termination of the study, an abbreviated CSR is planned.

The data that will

be summarized are full safety data, and data on disposition, baseline, demographics, exposure, and protocol deviations.

All analyses will be done based on data collected during the entire study including the core and the LTE periods. Where specified, a subset of analyses will comprise the Primary Analysis and summarize safety and tolerability data from the core period only.

There will be no statistical testing for any endpoints.

The statistical software, SAS® version 9.4 or above will be used for all summaries and analyses.

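### Should SAP 4.2 commit to repeating the Week 78 external-control comparison on data later than the 15 August 2022 cut?

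*SAP*

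**What the plan says.** SAP 2.1.2 describes secondary objectives that compare aducanumab with an external control. They come from a separate interim SAP, not from the protocol. On timing it states: "The corresponding primary clinical efficacy endpoint is change from baseline CDR-SB at Week 78". SAP 4.2 ties that comparison to one interim data cut: "This interim analysis used a data cutoff date of August 15th, 2022 (see Table 3) and comprised the primary efficacy analysis". It then says where the results go: "The analysis of the secondary objectives and endpoints will be summarized in the 221AD304 (EMBARK) CSR addendum". No cutoff date or database lock is attached to the addendum.

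Table 3 in SAP 4.1 describes the August 2022 cut. Approximately "1180 of 1675 (70%) participants from feeder studies 221AD301 and 221AD302 will have had an opportunity to complete" Week 78, and "All but one participant will have had an opportunity to complete the 221AD304 Week-52 visit". The table calls this the first analysis against an external control. It lists only analyses that "occurred prior to the completion of the core treatment period".

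SAP 4.2 also records that when early termination was announced on 19 September 2023, "all subjects had completed the Week 102 visit and only a few subjects had not completed the Week 118 follow-up visit". SAP 5.1 sets the limits of the document: "This statistical analysis plan (SAP) defines the analysis scope for the Primary Analysis and the Final Analysis". SAP 5.6 rules out efficacy analysis under this plan, and Table 11 gives early termination and the abbreviated CSR as the reason.

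**The concern.** The main efficacy comparison is read at Week 78, yet the cut labelled primary for efficacy was taken when about three in ten of the Phase 3 feeder participants could not yet have reached that visit. By the time this SAP was written, everyone had completed the core period, so the reason for the shortfall had gone. Nothing in the visible text says whether the addendum will report the August 2022 cut, the complete core data, or both.

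If only the early cut were reported, participants who enrolled later would contribute no Week 78 value. The comparison would be less precise, and if a longitudinal model is used, it would lean on that model for these participants more than it needs to. An unstated cut also leaves room to choose afterwards which result to show.

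**Working it through.** **Inputs**
- From SAP Table 3: N = 1675 participants from 221AD301 and 221AD302, of whom n = 1180 had a Week 78 opportunity on 15 August 2022; all but one participant had a Week 52 opportunity.
- From Protocol Table 2: Week 52 is Day 365 and Week 78 is Day 547.
- From SAP 4.2: all subjects were past Week 102 by 19 September 2023.
- Assumed, because neither document gives them: q, the fraction of those with an opportunity who have an observed Week 78 value (0.6 to 0.9); k, the control count divided by the aducanumab count once everyone has had the opportunity (0.25 to 2); r, the correlation between an earlier visit and Week 78 (0.6 to 0.8).

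**1. The plan's own percentage.** 1180/1675 = 70.4%, stated as 70%. The March 2022 row also agrees: 420/1675 = 25.1%, stated as 25%.

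**2. Size of the shortfall.** 1675 − 1180 = 495, or 29.6%. This counts opportunity to attend, not observed values.

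**3. When the shortfall closed.** 547 − 365 = 182 days. 15 August 2022 plus 182 days is 13 February 2023 (18 February with the 5-day visit window). All but one participant had reached nominal Week 78 by then, 218 days before 19 September 2023.

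**4. Values a later cut could add.** 495q is 297 at q = 0.6 and 446 at q = 0.9, on top of 1180q = 708 to 1062.

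**5. Effect on precision.** Assume equal outcome variance in both groups and the same q in early and late enrollers, so that q cancels. The ratio of the standard error of the difference at the early cut to its full-opportunity value is

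sqrt[(N/n + 1/k) / (1 + 1/k)], with N/n = 1.4195.

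- k = 0.25: 1.041
- k = 0.5: 1.068
- k = 1: 1.100
- k = 2: 1.131

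The ratio cannot exceed sqrt(1.4195) = 1.191, however large the control group. If a repeated-measures model uses an earlier visit, N/n becomes 1 + (1 − r²)(N/n − 1):

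- r = 0.6: 1.026 (k = 0.25) to 1.086 (k = 2)
- r = 0.8: 1.015 (k = 0.25) to 1.049 (k = 2)

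**6. Whether this SAP is where the cut should be stated.** Section 1 puts its focus on safety and tolerability. Section 5.1 limits it to the Primary and Final Analyses. In 4.2 the Primary Analysis means the core safety endpoints. Section 4.3 gives the Final Analysis a safety focus, and 5.6 excludes efficacy. The external-control comparison belongs to the interim SAP signed on 24 February 2023, and 4.2 mentions it only to point elsewhere. Two sentences in 4.2 break off where text has been removed, including the one that names the primary efficacy analysis, directly before the addendum sentence. A later cut could be stated in that removed text, in the interim SAP or in the addendum.

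**The case for a change.** The case for a change is a fair one. Calling an analysis the first suggests that another follows, while calling it the primary one suggests that none is needed, and 4.2 does not settle which. Protocol 5.2 records that in this program a larger, later dataset gave markedly different results from an early one, and that the sponsor came to regard the conclusions from the early one as wrong. Long-term efficacy is among the study's stated purposes. Naming a cut takes a sentence, and a rerun would use data already collected and methods already specified.

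What stands is that the visible text does not name the addendum's cut. The program history is a reason for the efficacy documents to be explicit about it, but it does not show that 221AD304 results would move. Nor does it make a safety SAP the place to commit to a new efficacy run. A repeat ordered here would be added after the August 2022 result may be known, in a study cut back to an abbreviated report. Showing both results with unchanged methods would limit that risk without removing it. Whether to repeat is a choice on which the sponsor could reasonably differ.

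**Conclusion.** No change to the plan is called for. The dates and percentages are right, and the visible part of SAP 4.2 is silent on the addendum's cut. That silence is a missing detail about an analysis which this SAP deliberately leaves to other documents, and following the visible text leads to no demonstrated wrong result. Table 3 stops at core completion and its wording is compatible with a later comparison.

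Even if the addendum reported only August 2022, the loss would be modest: a standard error 1.04 to 1.13 times its full-opportunity value, or about 1.02 to 1.09 times with an earlier visit modelled. These ranges rest on the assumed k and r, on equal variances, and on equal attendance in early and late enrollers. Any bias from enrollment timing cannot be sized from the documents. The core primary endpoints are safety endpoints and do not depend on this cut. Naming the addendum's cut would help the reader, but it would alter no analysis under this plan.

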4.3. Final Analysis

The final analysis of study 221AD304 will be performed at the end of the study after the last participant completes the last visit of the study and the final database is locked. The final analysis will include all data collected during the entire Study including both the core period and the LTE period.

Following the decision to terminate the study early, an abbreviated CSR is planned. As such, the final analysis will focus on evaluating the long-term safety and tolerability of aducanumab as described in the in Section 2.1.4. Disposition, baseline characteristics, demographics, exposure, and protocol deviation data will also be summarized to provide supporting information for the review of safety.

5. Statistical Methods for Planned Analyses

5.1. General Principles

This statistical analysis plan (SAP) defines the analysis scope for the Primary Analysis and the Final Analysis.

Summary tables will be presented using descriptive summary statistics. For continuous variables, summary statistics will generally include: number of subjects with data, mean, standard deviation, median, 25% percentile, 75% percentile, minimum and maximum. For categorical variables, this will generally include: number of subjects randomized or dosed, number with data, and the percent of those with data in each category.

All analyses will be summarized by safety analysis groups (0 dose of BIIB037, pre-treated with BIIB037 with 0 dose of 10 mg/kg, >0 dose of 10 mg/kg, subtotal of pre-treated with BIIB037, and overall total; analysis display SA in Appendix 9), unless otherwise specified. Where indicated, the analyses will be repeated by safety analysis group stratified by

Study: 221AD304 Version: 2.0

As noted in Section 1, due to the early termination of the study, an abbreviated CSR is planned.

The data that will

be summarized are full safety data, and data on disposition, baseline, demographics, exposure, and protocol deviations.

All analyses will be done based on data collected during the entire study including the core and the LTE periods. Where specified, a subset of analyses will comprise the Primary Analysis and summarize safety and tolerability data from the core period only.

There will be no statistical testing for any endpoints.

The statistical software, SAS® version 9.4 or above will be used for all summaries and analyses.

